### 8.3. Exploratory Endpoints

- CD28 and CD86 expression on myeloma cells will be assessed by flow cytometry at the time of trial enrollment and then at disease progression (or off study).
- Blood will be assayed for serum kynurenone and IL-6 levels.

## 9. DESIGN

This is a Phase II study designed to test the efficacy and safety of combining abatacept with the oral PI ixazomib + dexamethasone in multiple myeloma patients  $\geq 18$  years of age who have relapsed (or are primary refractory) following treatment with their first proteasome-inhibitor containing regimen (excluding prior treatment with ixazomib).

## 10. TREATMENT

### 10.1. Dosing and Administration

For the purpose of this study, 1 cycle = 28 days.

Treatment will be administered on an outpatient basis. All drugs will be stored, prepared and administered as detailed in their Package Inserts (see **Appendix F**). Study patients will be treated with:

**Abatacept:** A loading dose of abatacept (30 minute IV infusion) will be administered on Day 1 Cycle 1 (refer to **Table 1**), followed by 125 mg SQ on Day 2 and then 125 mg once weekly during Cycle 1 (i.e., Days 8, 15, 22) thereafter. After Cycle 1, abatacept 125 mg SQ is given on Days 1, 8, 15, 22 for all subsequent cycles.

**Table 1      Dose of Abatacept for IV Infusion in Adult Patients**

Body Weight of Patient	Dose	Number of Vials a
Less than 60 kg	500 mg	2
60 to 100 kg	750 mg	3
More than 100 kg	1000 mg	4

a Each vial provides 250 mg of abatacept for administration [taken from Orencia™ (abatacept) package insert: March 2017 revision].

Patients should be monitored for 30 minutes after the completion of the abatacept dose on Days 1 and 2 of Cycle 1 for clinical signs of toxicity. If the patient remains symptom free, no additional post-abatacept infusion monitoring is required. If the patient does develop symptoms, that patient should be monitored for 30 minutes (or longer if called for) after each abatacept administration.

### **Instructions for subcutaneous abatacept injection**

- Allow prefilled syringe and auto injector to warm to room temperature (for 30 to 60 minutes and 30 minutes, respectively) prior to administration.
- Inject into the front of the thigh (preferred), abdomen (except for 2-inch area around the navel), or the outer area of the upper arms.
- Rotate injection sites (1 inch or more apart): do not administer into tender, bruised, red, or hard skin.

***Ixazomib:*** 4 mg po on Days 1, 8, and 15 of a 28-day cycle.

***Dexamethasone:*** 40 mg po of Days 1, 8, 15, and 22 of a 28-day cycle. At the discretion of the treating physician, the weekly dose of dexamethasone may be split between two days.

Ixazomib and dexamethasone can be taken by the patient at home prior to the abatacept infusion, if the patient desires. Alternatively, the patient can bring their ixazomib and dexamethasone to the clinic and take it there.

***Acyclovir:*** 400 mg po BID will be prescribed by the study physician for varicella prophylaxis, as per NCCN recommendation for all patients receiving proteosome inhibitor-based therapies (35).

Patients will be treated until Stringent CR (see **Section 16.1**), disease progression, death, intolerable side effects or, Investigator judgment.

Reported adverse events (AEs) and potential risks are described in **Section 13**. Appropriate dose modifications are described in **Section 10.3**.

Treatment is intended for an outpatient setting. However, at the investigator's/physician's discretion, the participant may receive treatment as an inpatient, if deemed necessary.

### **10.2. Safety Lead-in**

The first 6 patients who have completed the first cycle of the treatment regimen without experiencing dose limiting toxicity (see Section 10.3) will comprise the safety lead-in group.

Patient data for the safety lead-in portion of the study will be discussed and monitored by The Early Phase Clinical Trials committee, which meets on a regular basis per the Roswell Park Data Safety Monitoring Plan.

After a minimum of 6 patients have completed at least one cycle of the treatment regimen, the study team will meet to examine the safety/tolerability of the combination. If 0 or 1 patient out of the 6 has experienced a drug related toxicity requiring treatment delay or suspension, an additional  $n_2=13$  patients will be enrolled to complete the study. Otherwise, the study will be suspended and the research team will meet to discuss possible safety concerns and will decide what actions to take with respect to study continuation (e.g., changes in treatment regimen/ dose modifications or discontinue the study).

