### **10.3. Definition of Dose Limiting Toxicity and Discontinuation of Therapy**

DLTs are AEs that occur within Cycle 1 and meet any of the following criteria:

1. Treatment-emergent Grade 4 or 5 AE related to ixazomib + abatacept + dex treatment (see exceptions listed in #4 below).

Roswell Park Protocol No.: I 47217

2. Treatment-emergent Grade 3 AE related to ixazomib + abatacept + dex (see exceptions listed in # 4 below).
3. Treatment-emergent Grade 3 seizures.

The above AEs are considered to be DLTs if they are judged probably or definitely associated with treatment. Should they occur, individual participants will be taken off study and no further injections will be given. Toxicity will be determined using the revised NCI Common Toxicity Criteria (CTC) version 5.0 for Toxicity and Adverse Event Reporting (<http://ctep.info.nih.gov>).

4. The following **will not** be considered DLTs:

- Non-hematologic AEs
  - Grade 3 fatigue lasting  $\leq$  7 days
  - Grade 3 or 4 fever or febrile neutropenia for  $\leq$  2 weeks
  - Grade 3 increase in transaminases for  $\leq$  2 weeks or Grade 4 increase in transaminases for  $\leq$  7 days
  - Grade 3 Tumor Lysis Syndrome (TLS) for  $\leq$  2 weeks
  - Grade 3 or 4 asymptomatic, non-hematological clinical laboratory abnormalities that return to  $\leq$  Grade 2 within 7 days or electrolyte abnormalities that resolve with replacement
  - Grade 3 diarrhea lasting  $\leq$  72 hours that does not require total parenteral nutrition (TPN), tube feeding, or hospitalization, and the toxicity resolves to less than grade 3 within 72 hours
  - Grade 3 nausea/vomiting lasting  $\leq$  72 hours that does not require total parenteral nutrition (TPN), tube feeding, or hospitalization, and the toxicity resolves to less than grade 3 within 72 hours
  - Grade 3 peripheral neuropathy
  - Grade 3 hyperglycemia, or Grade 4 that responds to insulin therapy
- Hematologic AEs
  - Grade 3 neutropenia of any duration or Grade 4 neutropenia lasting  $<$  14 days
  - Grade 3 or 4 lymphopenia
  - Grade 3 or 4 leukopenia
  - Grade 3 or 4 thrombocytopenia without bleeding or requiring platelet transfusion
  - Grade 3 or 4 anemia
  - Grade 3 or 4 B-cell aplasia and hypogammaglobulinemia

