### **19.3. Safety Cohort**

A safety lead-in cohort of  $n_1=6$  patients will be enrolled and, after each patient completes at least 1 cycle of the treatment regimen, the study will be suspended and evaluated for the safety/tolerability of the regimen. If 0 or 1 patient out of 6 has experienced a drug related toxicity requiring treatment delay or suspension, then an additional  $n_2=13$  patients are enrolled to complete the study. Otherwise, the study will be suspended and the research team will meet to discuss possible safety concerns and will decide what actions to take with respect to study continuation.

DLTs are AEs that occur within Cycle 1 and meet any of the following criteria:

1. Treatment-emergent Grade 4 or 5 AE related to ixazomib + abatacept + dex treatment (see exceptions listed in #4 below).
2. Treatment-emergent Grade 3 AE related to ixazomib + abatacept + dex (see exceptions listed in # 4 below).
3. Treatment-emergent Grade 3 seizures.
4. The following will not be considered DLTs:
  - o Non-hematologic AEs
    - Grade 3 fatigue lasting  $\leq 7$  days.
    - Grade 3 or 4 fever or febrile neutropenia for  $\leq 2$  weeks.
    - Grade 3 increase in transaminases for  $\leq 2$  weeks or Grade 4 increase in transaminases for  $\leq 7$  days.
    - Grade 3 Tumor Lysis Syndrome (TLS) for  $\leq 2$  weeks.
    - Grade 3 or 4 asymptomatic, non-hematological clinical laboratory abnormalities that return to  $\leq$  Grade 2 within 7 days or electrolyte abnormalities that resolve with replacement.
    - Grade 3 diarrhea lasting  $\leq 72$  hours that does not require total parenteral nutrition (TPN), tube feeding, or hospitalization, and the toxicity resolves to

less than grade 3 within 72 hours.

- Grade 3 nausea/vomiting lasting  $\leq$  72 hours that does not require total parenteral nutrition (TPN), tube feeding, or hospitalization, and the toxicity resolves to less than grade 3 within 72 hours.
- Grade 3 peripheral neuropathy.
- Grade 3 hyperglycemia or Grade 4 that responds to insulin therapy.
- Hematologic AEs
  - Grade 3 neutropenia of any duration or Grade 4 neutropenia lasting  $<$  14 days.
  - Grade 3 or 4 lymphopenia.
  - Grade 3 or 4 leukopenia.
  - Grade 3 or 4 thrombocytopenia without bleeding or requiring platelet transfusion.
  - Grade 3 or 4 anemia.
  - Grade 3 or 4 B-cell aplasia and hypogammaglobulinemia.

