#### 19.4. Primary Analyses

The primary objective is to determine the therapeutic efficacy (as measured by response rate) of abatacept + ixazomib + dexamethasone in multiple myeloma patients who have relapsed after treatment with their first proteasome inhibitor-containing regimen (excluding ixazomib) and have not been treated with a second proteasome inhibitor.

Previous studies have demonstrated a response rate of approximately 30% for ixazomib + dexamethasone as second line therapy in this patient population (34). We hypothesize that the proposed treatment combination (abatacept + ixazomib + dexamethasone) will improve the second-line response rate in this patient population. Therefore, we will test the following hypotheses:

$$H_0: \pi = 0.3$$

$$H_A: \pi > 0.3,$$

where  $\pi$  is the true response rate, using a one-sided Binomial exact test. A total of n=19 patients will be enrolled and if T=9 or more patients have a response, then the treatment combination will be considered promising; otherwise the treatment combination is not promising. Additionally, the response rate will be summarized using a 90% confidence interval obtained using Jeffrey's prior method.

**Replacement:** Patients that withdraw from the study prior to completing the first cycle of treatment due to toxicity, disease progression, or other treatment related reasons will be considered as 'non-responders' and included in the primary analysis.

Patients that withdraw from the study prior to completing the first cycle of treatment due to non-treatment related reasons will be considered 'unevaluable' for the primary outcome and will be replaced.

**Efficacy Analysis:** Responses to treatment will be measured by serum immunoglobulins, serum free kappa and lambda light chains, serum protein electrophoresis/immunofixation electrophoresis, and 24-hour urine protein electrophoresis/immunofixation. International uniform response criteria will be used. The anti-myeloma activity will be evaluated on an exploratory basis

Roswell Park Protocol No.: I 47217

and will be summarized using descriptive statistics or graphical methods. No formal comparison will be carried forth

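### Section 10.2 restricts the safety lead-in six to patients without a DLT, so read literally Cycle 1 DLTs cannot count toward the go/no-go rule; 19.3 conflicts with this but does not settle who is counted.

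*Combined protocol and SAP*

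**What the plan says.** Three sections bear on the lead-in gate.

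- **Section 10.2 (Safety Lead-in)** defines the group as "The first 6 patients who have completed the first cycle of the treatment regimen without experiencing dose limiting toxicity". It places the team's review at a different point, "After a minimum of 6 patients have completed at least one cycle of the treatment regimen", with no DLT-free condition. The go rule follows: "If 0 or 1 patient out of the 6 has experienced a drug related toxicity requiring treatment delay or suspension", then 13 more patients are enrolled. Otherwise the study is suspended and the team decides what to do.
- **Section 19.3 (Safety Cohort)** enrols six patients, again with no DLT-free condition. It evaluates them "after each patient completes at least 1 cycle of the treatment regimen", applies the same rule ("If 0 or 1 patient out of 6 has experienced a drug related toxicity requiring treatment delay or suspension") and lists the DLT criteria directly beneath it.
- **Section 10.3** says of DLTs: "Should they occur, individual participants will be taken off study and no further injections will be given".

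Two other passages matter. Section 4 caps enrolment at 19. Section 19.4 addresses early withdrawal for the efficacy analysis: "Patients that withdraw from the study prior to completing the first cycle of treatment due to toxicity, disease progression, or other treatment related reasons" are non-responders and stay in. No equivalent sentence exists for the safety gate.

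**The concern.** The go rule counts events among the six, and the only six that 10.2 defines are free of DLTs. A site following that definition replaces each DLT patient until it has six clean ones. A statistician following 19.3 starts from six enrolled patients. The two can reach different decisions on the same data.

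This gate stands before 13 further patients receive the combination, and Section 13 reports only one myeloma patient previously given abatacept. It is the only numeric gate on Cycle 1 toxicity. Taken literally, it omits the events that the protocol itself classes as dose limiting.

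The literal definition also strains the enrolment cap. Each DLT patient is additional to the six, so with d such patients a study that continues needs 6 + d + 13, which exceeds 19 whenever d is 1 or more.

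**Working it through.** **1. The plan's own figure.** The documents give no operating characteristics for the lead-in rule. The stated figure that rests on the 6 + 13 = 19 patients is 90% power at a 60% response rate, against a null of 30%, one-sided 0.10, with 9 or more responses required. Exact binomial: P(X ≥ 9 | 19, 0.3) = 0.084 and P(X ≥ 9 | 19, 0.6) = 0.912. The figure reproduces.

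**2. Assumptions for the gate.** Each patient has a Cycle 1 DLT with probability p or, exclusively of that, another drug-related toxicity requiring delay with probability t. The documents supply neither rate. I use p = 10%, 25%, 40% and t = 10%, 20%, 30%.

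**3. DLTs outside the literal 10.2 count.** The number of DLT patients, D, seen before six DLT-free patients accrue is negative binomial.

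- P(D ≥ 2) = 1 − (1 − p)^6 × (1 + 6p)
- p = 0.10: 1 − 0.5314 × 1.6 = 0.150
- p = 0.25: 1 − 0.1780 × 2.5 = 0.555
- p = 0.40: 1 − 0.0467 × 3.4 = 0.841

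**4. Going ahead with two or more uncounted DLTs.** Among DLT-free patients the other toxicity has probability t/(1 − p), independently of D. The joint probability is therefore P(D ≥ 2) × P(Bin(6, t/(1 − p)) ≤ 1).

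| t | p = 10% | p = 25% | p = 40% |
|---|---|---|---|
| 10% | 0.150 × 0.863 = 0.129 | 0.555 × 0.815 = 0.452 | 0.841 × 0.737 = 0.620 |
| 20% | 0.150 × 0.601 = 0.090 | 0.555 × 0.495 = 0.275 | 0.841 × 0.351 = 0.295 |
| 30% | 0.150 × 0.351 = 0.053 | 0.555 × 0.233 = 0.129 | 0.841 × 0.109 = 0.092 |

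**5. Comparator.** Suppose the first six enrolled are assessed and a DLT counts. This is an inferred reading of 19.3, not its text. DLTs alone then trigger the pause with probability P(Bin(6, p) ≥ 2) = 0.114, 0.466 and 0.767. Under literal 10.2 that probability is zero.

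**6. Knock-on for the primary rule.** If additional patients were enrolled, 19.4 would keep toxicity withdrawals in the analysis, so n would exceed 19. With the threshold left at 9, P(X ≥ 9 | n, 0.3) is 0.084 at n = 19, 0.113 at n = 20 and 0.148 at n = 21. These are nominal values: n is treated as fixed and every patient has the null response rate of 0.3.

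**The case against.** **The operative sentences point the other way.** The go rule follows the review sentence, which has no DLT-free condition, and 19.3 has none either. Most people would probably read it sensibly. That is fair as a guess about conduct, but it means setting aside the section's own definition of the group.

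**The DLT-free phrase is nearly redundant.** All three statements require completion of a cycle, and a patient taken off study for a DLT may never complete one. This stands, and it shows that deleting the phrase is not enough. No passage keeps such a patient in the denominator or says that removal is a treatment delay or suspension. A reader might infer that 19.3 clearly counts DLTs; that is the natural inference, but it is not stated.

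**There is another numeric rule.** Section 19.8 sets a continuous Bayesian suspension rule using the same DLT/AE criteria. It starts once the DLT assessment period is over and concerns chronic toxicity, so on its wording it does not bring the excluded Cycle 1 DLTs back.

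**Oversight continues.** A reader might infer that DLTs escape review altogether. They do not: "Patient data for the safety lead-in portion of the study will be discussed and monitored by The Early Phase Clinical Trials committee", the study team meets, the Data Safety Monitoring Committee reviews the study semi-annually (Section 20), and expedited SAE reporting applies (Section 17.5). None of these carries a numeric threshold for Cycle 1 DLTs.

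**The gate is not empty, and the sizes are assumed.** The rule counts delay-causing toxicity, which need not be a DLT, so a DLT-free six can still fail it. As the table shows, the more common such toxicity is, the less often the study would go ahead over uncounted DLTs. Section 10.3 exempts many Grade 3 and 4 events, and nothing in the documents supports a 40% DLT rate in particular.

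**Conclusion.** The inconsistency is real and is in the current text. Followed literally, 10.2 keeps every Cycle 1 DLT out of the lead-in count, a result that depends on no assumed rate. Sections 10.2, 10.3 and 19.3 together leave the denominator and the countable event undefined for a DLT patient.

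The size does depend on assumptions. Over the ranges examined, the chance of going ahead with two or more uncounted DLTs runs from 5% to 62%. The upper end needs a high DLT rate and little other delay-causing toxicity.

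Two stronger conclusions do not follow. Failing the count leads to suspension and a discretionary meeting, so the gap does not remove an automatic termination rule. Nor is the primary analysis flawed as planned: at n = 19 it holds its level. Only if literal 10.2 pushed enrolment past 19 with the threshold unchanged would the nominal level exceed 0.10. Because the defect sits in the numeric gate that precedes 13 further patients, it should be corrected before that gate is used.

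**What to change.** 1. Delete the DLT-free phrase from the lead-in definition in 10.2, so that 10.2 and 19.3 share one denominator: the six enrolled patients of 19.3, within the 19.
2. State that a patient who leaves during Cycle 1 for toxicity remains in that denominator, in line with how 19.4 treats such patients for efficacy.
3. Reconcile 10.2, 10.3 and 19.3 so that they say whether a DLT, or removal from study for one, is a countable event. Which clinical rule applies is for the sponsor and investigators to decide.

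This changes wording only. It adds no patients, visits or procedures, and keeping the six within the 19 leaves the primary rule as planned. The cost is a higher chance of a safety pause than under literal 10.2. If DLTs are counted and t is 10%, the chance of a pause is 1 − P(Bin(6, p + t) ≤ 1) = 34%, 68% and 89% at p = 10%, 25% and 40%. Under literal 10.2 it is 1 − 0.863, 1 − 0.815 and 1 − 0.737, or 14%, 19% and 26%. Section 19.3, on its natural reading, already carries the higher figures.

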**Table 3 Dose Modification Guidelines for Ixazomib**

Hematological Toxicities	Recommended Actions
Thrombocytopenia (Platelet Count)	
Platelet count less than 30,000/mm 	
 
Withhold ixazomib until platelet count is at least 30,000/mm^3.
 
Following recovery, resume ixazomib at the next lower dose.
 

Neutropenia (Absolute Neutrophil Count)	
Absolute neutrophil count less than 500/mm 	
 
Withhold ixazomib until absolute neutrophil count is at least 500/mm^3. Consider adding G-CSF as per clinical guidelines.
 
Following recovery, resume ixazomib at the next lower dose.
 

Non-Hematological Toxicities	Recommended Actions
Rash	
Grade † 2 or 3	
 
Withhold ixazomib until rash recovers to Grade 1 or lower.
 
Following recovery, resume ixazomib at the next lower dose.
 

Grade 4	
 
Discontinue treatment regimen.
 

Peripheral Neuropathy	
Worsening Peripheral Neuropathy over Baseline (Grade 2 with pain or Grade 3)	
 
Reduce ixazomib to the next lower dose. Reevaluate after 1 cycle, if improved or stable, continue at the reduced dose.
 

Grade 4 Peripheral Neuropathy	
 
Discontinue treatment regimen.
 

Other Non-Hematological Toxicities	
Other Grade 3 or 4 Non-Hematological Toxicities	
 
Withhold ixazomib. If attributable to ixazomib, resume at the next lower dose following recovery.
 

†Grading based on National Cancer Institute Common Terminology Criteria (CTCAE) Version 5.0.

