### **19.5. Secondary Analyses**

The secondary objectives include: 1) assessment of the abatacept + ixazomib + dexamethasone toxicity profile; 2) assessment of progression-free and overall survival.

The adverse events and drug related toxicities will be summarized by grade using frequencies and relative frequencies. The rate of grade 3 or higher toxicities that are probably or definitely related to abatacept will be reported with 90% confidence intervals obtained using Jeffrey's prior method.

Progression-free and overall survival will be summarized using standard Kaplan-Meier methods; where estimates of median survival and survival rates will be obtained with 90% confidence intervals

**Safety Analysis:** The NCI Common Terminology Criteria for adverse events (CTCAEv5.0) will be used to evaluate toxicity. We will consider a toxicity to be an adverse event that is possibly, probably or definitely related to treatment. The maximum grade of toxicity for each category of interest will be recorded for each patient and the summary results will be tabulated by category and grade. Regimen limiting toxicities (RLT) include any Grade 3 or greater toxicity probably or definitely related to abatacept. The rate of grade 3 or higher toxicities that are probably or definitely related to abatacept will be reported with 90% confidence intervals obtained using Jeffrey's prior method.

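### The lead-in safety rule does not count the DLTs defined in Section 10.3, and Sections 10.2 and 19.3 disagree on which six patients it is applied to

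*Combined protocol and SAP*

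**What the plan says.** - **Who is counted, Section 10.2.** The lead-in group is "The first 6 patients who have completed the first cycle of the treatment regimen without experiencing dose limiting toxicity".
- **Who is counted, Section 19.3.** Six patients are enrolled and evaluated after each has completed at least one cycle. Nothing requires them to be free of DLT.
- **What is counted.** Section 10.2: "If 0 or 1 patient out of the 6 has experienced a drug related toxicity requiring treatment delay or suspension", a further 13 patients are enrolled. Section 19.3: "If 0 or 1 patient out of 6 has experienced a drug related toxicity requiring treatment delay or suspension", with the same consequence. Otherwise the study is suspended and the research team decides how to proceed.
- **DLTs.** Section 10.3 defines them as Cycle 1 events of Grade 3 or above, with a list of exemptions. Section 19.3 repeats that list directly below its rule. For a patient with a DLT, 10.3 says: "Should they occur, individual participants will be taken off study and no further injections will be given".
- **Holds.** Section 10.4, whose heading covers both dose modifications and treatment delays, contains Table 3. For Grade 2 or 3 rash the table says "Withhold ixazomib until rash recovers to Grade 1 or lower". It also withholds ixazomib for other Grade 3 or 4 non-hematological toxicities.
- **Attribution.** For DLTs: "The above AEs are considered to be DLTs if they are judged probably or definitely associated with treatment". For the safety analysis in 19.5: "We will consider a toxicity to be an adverse event that is possibly, probably or definitely related to treatment". The lead-in rule says only that the toxicity is drug related.

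**The concern.** A lead-in of six patients is there to answer whether the combination is tolerable before 13 more are exposed. The protocol writes out a detailed standard for that question, and then the rule counts something else. The two can diverge in both directions. Events that the protocol has decided are not dose limiting can trip the rule. The events it regards as dose limiting can fall outside the count, because the patient leaves the study rather than being delayed and because 10.2 does not place that patient among the six.

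This is the only pre-specified study-level safety decision covering Cycle 1. Section 19.7 plans no interim analysis, and the Bayesian monitoring in 19.8 begins after the DLT period. Section 13 states that abatacept has not previously been combined with standard chemotherapy. Two teams applying the text to the same patients could reach opposite decisions.

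**Working it through.** **1. The plan's own figure.** No operating characteristics are stated for the lead-in rule. The one stated design figure is 90% power with n = 19 and at least 9 responses (19.1, 19.4). Exact binomial: P(X ≥ 9 | 19, 0.3) = 0.0839 and P(X ≥ 9 | 19, 0.6) = 0.9115. This reproduces, 6 + 13 = 19, and it does not bear on the point.

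**2. Which six.** Under 10.2, if k patients have a DLT before six have finished Cycle 1 without one, 6 + k have been treated and the rule looks at 6. Section 19.4 counts patients who withdraw in Cycle 1 for toxicity as non-responders in the primary analysis. Enrolling 13 more would then give 6 + k + 13 = 19 + k, above the maximum of 19 in Section 4 whenever k ≥ 1. Under 19.3 the k patients are among the six.

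**3. Which event.**

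| Cycle 1 event, drug related | Status in 10.3 | Consequence | Counted by the rule? |
|---|---|---|---|
| Grade 2 rash | Below DLT grade | Ixazomib withheld | Yes, if a hold is a delay |
| Grade 3 fatigue, 7 days or less | Exempt | Ixazomib withheld | Yes, if a hold is a delay |
| Grade 3 hyperglycemia | Exempt | Ixazomib withheld | Yes, if a hold is a delay |
| Non-exempt Grade 3 or 4 | DLT | Off study | Not literally; outside the six in 10.2 |
| Grade 5 | DLT | Death | Not literally; outside the six in 10.2 |

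The last two rows assume no hold came before removal or death.

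**4. Size.** The study is suspended if 2 or more of 6 patients have the counted event. With per-patient probability p:

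P(suspend) = 1 − (1 − p)^6 − 6p(1 − p)^5

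For p = 0.10: 1 − 0.5314 − 0.3543 = 0.114. The documents give no event rates. The DLT rate d and the non-DLT hold rate q below are assumptions, taken as independent.

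| p | 0.05 | 0.10 | 0.20 | 0.30 | 0.40 |
|---|---|---|---|---|---|
| P(suspend) | 0.033 | 0.114 | 0.345 | 0.580 | 0.767 |

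- *Section 10.2 read literally, holds counted.* The six are DLT-free, so p = q whatever d is. For q from 0.10 to 0.40, P(suspend) runs from 0.114 to 0.767 with no DLTs at all. For q = 0 it is 0, even at d = 0.40.
- *DLTs counted in six enrolled patients.* Here p = d, so P(suspend) = 0.767 at d = 0.40.
- *Section 19.3 read literally.* With six enrolled patients and removal for a DLT not counted, p = q(1 − d). At q = 0.30 and d = 0.40, p = 0.18 and P(suspend) = 0.296, against 0.580 at d = 0. More DLTs make suspension less likely.
- *Broad reading, DLTs and holds both counted in six enrolled patients.* Here p = 1 − (1 − d)(1 − q). At d = 0.10 and q = 0.10, 0.20, 0.30, p = 0.19, 0.28, 0.37 and P(suspend) = 0.320, 0.536, 0.717, against 0.114 for DLTs alone.

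**5. Changing the event alone.** If the 10.2 rule counted DLTs while its opening sentence stayed, it would count DLTs among patients selected for having none: p = 0 and P(suspend) = 0.

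**The case against.** The best defence is that a broad tolerability trigger is a legitimate choice for an untried combination, and that tripping it has limited consequences. The study is suspended for discussion, not terminated, and 19.3 pauses it for evaluation after six patients in any case. The review covers safety and tolerability generally, the early-phase committee follows the lead-in, and the data safety monitoring committee reviews the study semi-annually. A reader might infer from the literal rule that DLTs or deaths would go unexamined; those provisions do not support that. It remains true that the pre-specified count need not include them.

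A second defence is that suspension can be read to include permanent removal. That is possible, but Table 3 separates withholding from discontinuing, and 10.2 itself treats suspending and discontinuing the study as different things. This reading also does nothing for the DLT-free cohort sentence in 10.2.

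Third, the text never says that holding ixazomib alone is a treatment delay. Table 3 gives recommended actions, and no abatacept modification is planned. The heading of 10.4 favours that reading without settling it, so this half of the point is conditional.

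The platelet and neutrophil thresholds in Table 3 are left out of the argument. The documents do not give the grade cut-offs, and 3.1 admits patients with platelets from 25,000/mm³, below the 30,000/mm³ hold threshold, so a low count need not be drug related.

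**Conclusion.** The point stands. As written, the 0-or-1-of-6 rule does not count the protocol's own DLTs, and 10.2 and 19.3 define the six differently. The conflict over the six needs no assumption. That non-DLT events count depends on treating an ixazomib hold as a delay. That DLTs escape the count in 19.3 depends on the literal wording; in 10.2 it follows from the cohort definition as well.

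The sizes are illustrations under assumed rates: suspension for review in 11% to 77% of trials with no DLTs and hold rates of 10% to 40%; and 0% against 77% with no holds and a 40% DLT rate. They are not predictions for this regimen.

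Two stronger readings are not supported. A reader might infer that the DLT criteria drive no suspension rule anywhere, but 19.8 applies them with a table of counts after the DLT period; the gap is confined to the lead-in. A reader might also infer that failing the rule ends the trial, but it leads to suspension and review.

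**What to change.** Reconcile Sections 10.2, 10.3, 10.4.2 (Table 3) and 19.3 so that one named event, counted in one defined set of six patients, governs the rule in the same words in 10.2 and 19.3. Specifically:

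- Revise the opening sentence of 10.2 so that patients with a DLT, permanent discontinuation for toxicity or toxic death in Cycle 1 are not dropped from the denominator. Without this, substituting DLT for the counted event would make the 10.2 count always zero.
- State whether those outcomes count, whether a hold of ixazomib alone counts, and whether holds for events on the 10.3 exemption list count.
- State the time window and attribution level of the counted event, since 10.3 and 19.5 use different attribution levels.

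Which event governs is the sponsor's decision. The cost is a few sentences in two sections, with no extra procedures. Giving P(suspend) for the chosen event over a range of rates, as in the table above, would show what the rule can detect.
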